b. Full physical examination only at Screening and Day 393 (or EOS). Targeted physical exam at other indicated visits.

INO-4800 Inovio Pharmaceuticals, Inc.

- c. In women of childbearing potential. Urine pregnancy test at all indicated visits.
- d. Intradermal injection(s) in skin preferably over deltoid region, or alternately over anterolateral quadriceps region, followed by EP at Day 0 and Day 28.
- e. Following administration of INO-4800 or placebo, a subset of sites will be required to download EP data from the CELLECTRA® 2000 device and provided to Inovio.
- f. AEs to be collected from time of consent to Day 56; SAEs, MAAEs, and AESIs to be collected from time of consent to EOS.
- g. On Day 0, cellular sampling requires 64 mL of whole blood prior to 1st dose. At all other time points, collect 32 mL of whole blood. Cellular samples will be collected at selected clinical sites (estimated to include 711 subjects)
- h. On Day 0, humoral sampling requires a total of 17 mL of whole blood (two 10-mL red top serum collection tubes, each 8.5 mL of whole blood, to produce four serum aliquots of 2 mL each). At all other time points, collect 8.5 mL of whole blood in a single 10-mL red top serum collection tube to produce two serum aliquots of 2 mL each.
- i. SARS-CoV-2 antibody. Screening samples will be tested in the clinic via rapid test to detect antibodies against the Spike protein. Samples collected pre-dose Day 0 and at subsequent timepoints will be tested at a study-designated lab to detect antibodies against the Nucleocapsid protein.
- j. The Day 0 RT-PCR results will not be required prior to dosing on that day.
- k. Day 42 visit must occur at least 10 days after Day 28 visit.
- I. Subjects will be evaluated during a "COVID-19 assessment visit" when acute COVID-19 is suspected. The assessment visit may be performed in the clinic, subject's vehicle, or at a home visit and should be completed within 3 days of symptom onset or within 3 days of a positive result of a SARS-CoV-2 test.
- m. For subjects with virologically-confirmed SARS-CoV-2 infection during the trial, a convalescent visit should be scheduled approximately 28 days after symptom onset, or in the absence of symptoms, after the collection date of any specimen testing positive for SARS-CoV-2 RT-PCR. If acute symptoms are ongoing the site should follow up with the subject via phone call or unscheduled visit after symptom resolution or stabilization

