^bEU commission guideline on the SmPC September 2009 [64]

^c Brief muscle contractions may occur and could be uncomfortable

1.4.2.2 Theoretical Risks of INO-4800 Delivered ID followed by EP using the CELLECTRA[®] 2000 Device

The following adverse events have been observed at least once, as of Dec. 31, 2020, across all clinical trials with Inovio DNA products delivered intradermally followed by EP using the CELLECTRA[®] 2000 device:

- Allergic reaction
- Anxiety
- Creatine phosphokinase (CPK) elevations that are transient
- Injection site infection, paresthesia, hypoesthesia, hematoma, or scab
- Vasovagal reaction, lightheadedness or dizziness.

The following events have not been observed, as of Dec. 31, 2020, in any subject or any clinical trials with Inovio DNA products delivered intradermally followed by EP using the CELLECTRA[®] 2000 device. While considered theoretical and unlikely to occur, any occurrence of these events should be reported to the Sponsor during this trial:

 Antibody-dependent enhancement of disease (i.e., potential for greater respiratory disease upon exposure to SARS-CoV-2 due to priming of immune cells from prior

INO-4800	COVID19-311
Inovio Pharmaceuticals, Inc.	Clinical Protocol

vaccination. Although observed in nonclinical models for vaccines against other viruses such as SARS, the occurrence or observation of antibody-dependent enhancement of the disease with COVID-19 vaccines in humans remains unknown)

- Cardiac arrhythmias (product-related); Please note that "ICD or pacemaker (to prevent a life-threatening arrhythmia) that is located ipsilateral to the deltoid injection site (unless deemed acceptable by a cardiologist)" is an exclusion criterion ('j') in this protocol;
- Death (product-related);
- Disruption of function of implanted electronic medical device(s); Please note that "ICD or pacemaker (to prevent a life-threatening arrhythmia) that is located ipsilateral to the deltoid injection site (unless deemed acceptable by a cardiologist)" is an exclusion criterion ('j') in this protocol;
- Effects on fetus and/or pregnancy; Please note inclusion criterion in this protocol which requires use of medically effective contraception in women of childbearing potential;

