4.2.2 PHASE 3 SEGMENT

- Acute febrile illness with temperature ≥100.4°F (38.0°C) or acute onset of upper or lower respiratory tract symptoms (e.g., cough, shortness of breath, sore throat) within 72 hours prior to Day 0 dosing;
- Positive serologic test for SARS-CoV-2 at Screening (after approximately 402 subjects positive for SARS-CoV-2 serologic test are randomized, this criterion will apply to all remaining subjects);
- c. Pregnant or breastfeeding, or intending to become pregnant or intending to father children starting from the Screening visit until the last dose;
- d. Positive urine pregnancy test during screening or immediately prior to dosing;
- e. Known history of uncontrolled HIV based on a CD4 count less than 200 cells/mm³ or a detectable viral load within 3 months prior to screening;
- f. Is currently participating or has participated in a study with an investigational product within 30 days prior to Day 0 (documented receipt of placebo in a previous trial would be permissible for trial eligibility);
- g. Previous or planned receipt of an investigational (including Emergency Use Authorization (EUA) or local equivalent authorization) or licensed vaccine for prevention or treatment of COVID-19, MERS or SARS (documented receipt of placebo in previous trial would be permissible for trial eligibility);
- h. Immunosuppression as a result of underlying illness or treatment including:
 - Primary immunodeficiencies (conditions including hypothyroidism, Hashimoto's thyroiditis and vitiligo are allowed);
 - Long term use (≥7 days) of oral or parenteral glucocorticoids at a dose of ≥20 mg/day of prednisone equivalent (use of inhaled, topical, nasal, otic, and ophthalmic corticosteroids are allowed) in the past 6 months;
 - Current or anticipated use of disease modifying doses of systemic anti-rheumatic drugs (e.g., azathioprine, cyclophosphamide, cyclosporine, methotrexate) and biologic disease modifying drugs such as TNF-α inhibitors (e.g., infliximab, adalimumab or etanercept) or others;

INO-4800	COVID19-311
Inovio Pharmaceuticals, Inc.	Clinical Protocol

- History of solid organ or bone marrow transplantation;
- History of or current receipt of any other clinically significant immunosuppressive drugs
- Diagnosis of an autoimmune disease that may jeopardize the safety of the subject or require therapy that would interfere with study assessments or endpoint evaluation, or otherwise impact the validity of the study results.

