6.1.2.1 Day 0 and Day 28 (Dosing Visits)

The following evaluations will be performed on **Day 0 and Day 28 prior to dose administration**:

Both Phase 2 and Phase 3 segments:

- Collect all present and/or new or ongoing AEs (Section 6.4.4);
- Document any present conditions and concomitant illnesses;
- Record current concomitant medications/treatments (Section 6.4.6);
- Obtain any updates to medical history, surgical history (including all clinically significant procedures within the past 12 weeks), present conditions and concomitant illnesses (Day 0 visit only) (Section 6.1.1.1);
- Targeted physical examination (Section 6.4);
- Record vital signs (Section 6.4);
- Collect urine for urine pregnancy test (Section 6.4);
- Collect blood for HIV serology (Day 0 visit only) (Section 6.4);
- Collect whole blood and serum for cellular and humoral immunology assessment (Day 0 visit only) (Phase 3 cellular immunology collection at selected sites only) (Section 6.5);
- Review restrictions for injection and EP (Section 6.4.7);
- Randomize subject (instructions to be provided under separate cover) (Day 0 visit only).

Phase 2 segment only:

- Collect blood for CBC with differential and serum chemistry (Section 6.4);
- Collect urine for routine urinalysis (Section 6.4);
- Collect diary from Day 0 dose (Day 28 visit only).

Phase 3 segment only:

- Collect serum for SARS-CoV-2 antibody testing (Section 6.4.8);
- Collect nasopharyngeal swabs for SARS-CoV-2 RT-PCR (Day 0 only) (Section 6.4.8);
- Collect diary from Day 0 dose during Day 28 visit only (for selected sites only).

The following evaluations will be performed on Day 0 and Day 28 after IP plus EP administration:

- Collect any new AEs (Section 6.4.4);
- Download EP Data (for selected sites only);
- Provide supplies for subject to use at home, as required (e.g. thermometer, wound guide);
- Phase 2 segment: Distribute diary;
- Phase 3 segment, for selected sites: Distribute diary.

6.1.2.2 **Post-dose phone calls**

Phase 2 segment: Day 7 and Day 35 Phase 3 segment: Day 14

The following evaluations will be performed at this visit:

- Collect all present and/or new or ongoing AEs (Section 6.4.4);
- Document any present conditions and concomitant illnesses;
- Record current concomitant medications/treatments (Section 6.4.6);

Phase 2 segment only:

• Review diary (Section 6.4).

Phase 3 segment only:

• Review diary (for selected sites)(Section 6.4);

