Urine samples will be tested by dipstick for glucose, protein, and hematuria at Screening (Phase 2 segment only) and at visits specified in the Schedule of Events (Tables 3 and 4). If abnormal (presence of protein, hematuria, or glucose \geq 1+), a microscopic examination should be performed.

INO-4800	COVID19-311
Inovio Pharmaceuticals, Inc.	Clinical Protocol

Serology:

HIV antibody or rapid test will be performed at Day 0 only.

Antibodies to SARS-CoV-2 will be measured at Screening in the clinic using a rapid test which detects Spike protein antibodies and at pre-dose Day 0 and subsequent visits via testing at a study-designated lab which detects antibodies to Nucleocapsid protein. Timepoints are specified in the Schedule of Events (Tables 3 and 4).

Pregnancy Testing:

Pregnancy testing will be performed on women of childbearing potential (WOCBP). All women will be assumed to be of childbearing potential unless they are:

- Women who are post-menopausal as defined by reported spontaneous amenorrhea for ≥ 12 months;
- Women who are surgically sterile or have a partner who is sterile (i.e., vasectomy in males or tubal ligation, absence of ovaries and/or uterus in females). In the case of a vasectomy, subjects should wait six (6) months post-vasectomy to be considered sterile.

Phase 2: For WOCBP, a serum pregnancy test will be obtained at Screening and a urine pregnancy test will be performed immediately prior to any dosing and at the subject's last visit.

Phase 3: For WOCBP, a urine pregnancy test will be obtained at Screening and will be performed immediately prior to any dosing.

A negative result for urine β -HCG (test must have a sensitivity of at least 25 mlU/mL) must be available prior to each administration of IP. If the β -HCG test is positive, indicating that the subject is pregnant prior to completing the specified dose regimen, then no further IP will be administered. Every attempt should be made to follow pregnant subjects for the remainder of the study and to determine the outcome of the pregnancy (see Section 7.12).

DIARY

Diaries will be implemented in the Phase 2 segment of the protocol and at selected sites (estimated to include 711 subjects) in the Phase 3 segment. Subjects will be provided a diary to record the following solicited local and systemic AEs:

- Oral temperature and time taken (each daily entry before 11:59 pm)
- Solicited systemic symptoms
- Solicited local injection site symptoms
- Concomitant medications

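### Section 6.4 counts a partner's sterility as making a woman not of childbearing potential, so Phase 3 pregnancy tests are not required for her and exclusion d cannot operate; a sentence in the same section conflicts with this

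*Protocol*

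**What the plan says.** All references are to version 7.0 of the protocol.

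- **Scope of testing (Section 6.4, Pregnancy Testing).** "Pregnancy testing will be performed on women of childbearing potential (WOCBP"). The default is wide: "All women will be assumed to be of childbearing potential unless they are" in one of two listed groups, the post-menopausal and the sterile.
- **The second group.** It opens "Women who are surgically sterile or have a partner who is sterile (i.e., vasectomy in males or tubal ligation" and continues with absence of ovaries or uterus. The one added condition is "In the case of a vasectomy, subjects should wait six (6) months post-vasectomy to be considered sterile".
- **Phase 3 tests.** Section 6.4 prescribes a urine test at Screening and just before any dose, for women of childbearing potential. Table 4 footnote c agrees: "In women of childbearing potential. Urine pregnancy test at all indicated visits".
- **Eligibility.** Inclusion f in Section 4.1.2 requires one of three reproductive conditions, and f.2 is met by a sterile partner alone. Exclusion d in Section 4.2.2 is "Positive urine pregnancy test during screening or immediately prior to dosing". Inclusion b and exclusion c bar pregnancy without mentioning a test.
- **The conflicting sentence.** Later in the same block, Section 6.4 says that a negative urine β-HCG result has to be in hand ahead of every administration of IP. It does not restrict this to women of childbearing potential.
- **Visit lists.** Section 6.1.2.1 has "Collect urine for urine pregnancy test (Section 6.4"), and Section 6.1.1 has a similar line for Screening.

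**The concern.** Two different questions are answered with the same words. Inclusion f.2 asks whether a participant is adequately protected against conceiving during the dosing period, and a sterile partner is offered there as one answer. Section 6.4 asks whether a woman could be pregnant, which decides whether she is tested. A partner who is sterile now does not establish that a woman who is herself fertile is not already pregnant at Screening.

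What is at stake is a safety check. The protocol excludes pregnant women, gives no further IP after a positive test, and lists effects on a fetus or pregnancy among its theoretical risks. Section 1.4.2.2 answers that risk by pointing to an inclusion criterion that "requires use of medically effective contraception in women of childbearing potential". For the woman described here that criterion is met without contraception of her own, and the Section 6.4 definition also removes the requirement to test her. An unrecognised pregnancy could therefore pass both dosing visits with nothing in the exemption prompting anyone to look for it.

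**Working it through.** There is no figure of the plan to reproduce. The check follows one participant through the text: a fertile woman in Phase 3 whose partner is sterile (if by vasectomy, at least six months earlier).

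1. **Can she enrol?** Yes. Inclusion f asks for one of its options, and f.2 is satisfied by the partner's status. Option f.3 (contraception) is then not needed.
2. **Is she of childbearing potential under Section 6.4?** No. The default would include her, but the second exception removes her because of her partner. Section 6.4 attaches only the six-month vasectomy condition; it asks for no baseline test.
3. **Which tests are required of her?** The Phase 3 rule in Section 6.4 and Table 4 footnote c both cover only women of childbearing potential:

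| | Screening | Day 0 | Day 28 | Tests required | Planned doses |
|---|---|---|---|---|---|
| Woman of childbearing potential | 1 | 1 | 1 | 3 | 2 |
| Fertile woman with sterile partner | 0 | 0 | 0 | 0 | 2 |

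4. **Does exclusion d still work?** It is triggered only by a positive result. With no test required, it has nothing to act on.
5. **What else protects her?** Inclusion b and exclusion c bar a known pregnancy, and Section 7.12 repeats this. Section 7.12 also stops further IP if the site learns of a pregnancy after the first dose. None of these calls for a test.
6. **Does other text restore the test?** There are two candidates.
   - The β-HCG sentence in Section 6.4 has no limit to women of childbearing potential. Read literally it covers her before both doses, and it would also cover men. Read as part of a block whose opening confines testing to women of childbearing potential, it does not cover her. The text does not settle which reading applies.
   - The lines in Sections 6.1.1 and 6.1.2.1 are also unqualified, but both refer back to Section 6.4, so they take their scope from the rule in question and decide nothing alone.

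Section 6.4 therefore exempts her in one place and, on a literal reading, requires a negative result from her in another. Footnote c sides with the exemption.

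The same definition governs Phase 2, where Section 6.4 again limits testing to women of childbearing potential while Table 3 footnote e carries no such limit. Phase 3 is the clearer case, because footnote c repeats the limit explicitly.

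**The case against.** The strongest reply is the β-HCG sentence: if a negative result is needed before every administration, this woman is tested whatever the definition says. That has force. It means one cannot state as fact that such women are dosed without a test, which is what a reader might infer from the definition and footnote c alone. The documents support only the statement that the scheduled tests are not required for her under one rule, while another sentence may require them. The reply does not remove the problem. If the sentence applies to her, it contradicts the exemption and footnote c; if it does not, the gap is there.

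Second, pregnancy is barred elsewhere. This also stands in part: a pregnancy that is known or disclosed is excluded before dosing, so it would be too strong to say that any pregnancy would be found only after exposure. What is lost is the means of finding one that is not known.

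Third, the risk is modest. Section 1.4.2.2 describes fetal effects as theoretical, unlikely and not observed, and names contraception rather than testing as the mitigation. The subgroup also consists of women whose partners are sterile. These points limit the weight of the finding but do not make the definition sound.

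A reader might also want a headcount. Table 2 plans 5,001 + 201 = 5,202 Phase 3 subjects aged 18-50, but the protocol gives neither the share who are women nor the share relying on a sterile partner. Any figure would rest on assumptions for both, and it would count women for whom tests are not required rather than pregnancies. Allocation is 2:1, so about a third of them would receive placebo. Nor does the protocol say how a partner's sterility is established, so it cannot be said to rest on self-report.

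**Conclusion.** The point holds as an error of definition with a contradiction beside it. Section 6.4 uses the partner's sterility to decide whether the woman herself could be pregnant. Under that definition and footnote c, 0 of the 3 Phase 3 tests are required for a fertile woman with a sterile partner, and exclusion d cannot operate for her. Inclusion b and exclusion c continue to bar a known pregnancy. The unqualified β-HCG sentence conflicts with the exemption, so sites can read Section 6.4 either way.

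This rests on the plain wording and on no numerical assumption. The number of women affected is not given and cannot be derived from the document. Power, type I error and the efficacy estimate are not touched. The point matters because it concerns a safety check before dosing and is cheap to put right.

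**What to change.** Reconcile the following so that they state one rule: the list in Section 6.4 of women not of childbearing potential, including its vasectomy sentence; the β-HCG sentence in the same block; Table 4 footnote c; the pregnancy-test lines in Sections 6.1.1 and 6.1.2.1; and exclusion d in Section 4.2.2. In doing so, keep the sterile-partner option in inclusion f.2, which concerns contraception, separate from the definition of who is tested, and make the β-HCG sentence say whom it covers. Which women are to be tested is for the sponsor and its clinical advisers to settle; the request is that the protocol give a single consistent answer before each dose.

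The cost is amendment wording. Depending on how the texts are reconciled, there may be at most three urine tests, already in the schedule, for each woman in a subgroup that is probably small but whose size the protocol does not give. No visit or procedure is added.

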6.4.1 INTRADERMAL INJECTION AND EP

Phase 2 and Phase 3 segments:

A complete administration procedure is defined as an ID injection (formation of a wheal) of IP followed by insertion of the ID Array needles (electrodes) through the skin and into the wheal followed by delivery of four electroporation pulses. This procedure is broadly described as administration because it involves more than the injection of a drug.

Only if the deltoid area is not a suitable location for administration (see exclusion criterion 'j'), the ID injection can then be administered above the lateral quadriceps followed immediately by EP. IP must not be given within 2 cm of a tattoo, scar, keloid, or active lesion/rash. Also, ID injection followed immediately by EP must not be performed on the skin of an extremity which has any metal implants or implantable medical device (e.g., surgical rods, pins or joint replacements). If a subject has an implanted cardiac defibrillator or pacemaker, ID injection/EP must not be performed above the deltoid muscle on the same side of the body where the device is located.

There are three steps that must be performed as part of the administration procedure:

- 1. Injection of IP (INO-4800 or placebo)
- 2. Insertion of the array into the subject's skin
- 3. Pressing the trigger button on the EP applicator

Table 9 below is provided as guidance on how to appropriately complete the procedure when injection of IP has occurred, but the subject did not receive EP.

Table 9: Guidance for how to manage an incomplete administration after IP has	
been injected	

Was IP injected?	Was the array inserted into skin?	Was trigger button pressed?	Action
Yes	Yes (if array gets dislodged before the trigger button is pressed, the same array may be re-inserted)	No	If the drug injection wheal is discernable, EP should be attempted at the site of drug injection to complete the procedure
Yes	No	Yes	If the drug injection wheal is discernable, EP should be attempted at the site of drug injection to complete the procedure
Yes	No	No	If the drug injection wheal is discernable, EP should be attempted at the site of drug injection to complete the procedure

Reinjection of IP (i.e. protocol-specified IP has already been delivered) is not permitted. Delivery of a second electroporation in tissue is not permitted.

Training will be provided by the Sponsor on use of the device.

Phase 2 segment:

Subjects will receive a two-dose regimen of one or two 1.0 mg ID injections of INO-4800 or placebo in a volume of ~0.1 mL in an acceptable skin location for injection and subsequently followed immediately by EP of each injection site with CELLECTRA[®] 2000 at Day 0 and Day 28. For subjects assigned to receive two injections + EP at each dosing visit, the two injections must be performed in acceptable locations on two different limbs.

Phase 3 segment:

Subjects will receive a two-dose regimen of two 1.0 mg ID injections of INO-4800 or placebo in a volume of ~0.1 mL in an acceptable skin location for injection on different limbs and subsequently followed immediately by EP of the injection site with CELLECTRA[®] 2000 at Day 0 and Day 28.

